13. APPENDIX 1 – EXTENSION OF WILCOXON RANK-SUM TEST FOR CLUSTERED DATA

Adapted from Lehmann, 2006:

To compare each one of the treatment arms to the placebo arm separately, perform the following steps:

1. Each FF category at baseline will be defined as a separate cluster.
2. Within each cluster, rank all values (treatment and placebo together)
3. Calculate w_i which is the sum of ranks of the treatment group in each cluster separately.

$$W = \sum_{i=1}^M w_i$$

4. Calculate W while M is the total number of clusters.
5. The best way to test W is by using a **permutation test**. This may be computationally too complex to apply. If so, there is a normal distribution approximation we can use but it is less accurate, especially in our small sample so, if possible, we advise to try and use the permutation test.

The permutation should be performed so we protect the data of each cluster separately and also protect the cluster design of the sample.

More specifically, Let us define:

n_i - the number of observations in cluster i .

n_{i0} - the number of observations in cluster i , in the placebo arm.

n_{i1} - the number of observations in cluster i , in the treatment arm.

Each permutation will be calculated by randomly sampling n_{i1} values within each cluster from the n_i values available and calculating the rank sum of those values. Going over all possible permutation of the data under this design.

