## 8. STUDY DRUGS

### 8.1 Randomization

Subjects will be randomized to one of three treatment groups using a permuted block randomization algorithm supplied by a statistician blinded to patient data.

NASH without insulin resistance or diabetes may be clinically different to NASH with pre-diabetes or diabetes. Equal numbers of patients in each treatment arm is targeted. Randomization will be proportional (1:1:1) and stratified by Baseline HBA1C  $\leq 6.0$  or  $>6.0 - 9.0$ . (See [Section 7.2.2](#) and the Study Reference Manual)

Additionally, to ensure baseline Hepatic Fat Fraction (HFF) would not be a confounding factor, subjects will be stratified for baseline HFF according to the following groups  $\leq 10\%$ ,  $10\% < X \leq 20\%$ ,  $20\% < X < 30\%$  and  $\geq 30\%$ .

If a subject discontinues from the study, the randomization code will not be reused, and the subject will not be allowed to re-enter the study.

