7.2 Primary efficacy analyses

The hepatic fat fraction will be summarised and tabulated for the Baseline and Week 24 visits along with change from Baseline by randomised treatment group. Change in hepatic fat fraction from Baseline will be analysed using analysis of variance on the ITT, PP and FAS populations, where the model will include the treatment group and another subgrouping variable. As determined by baseline values, hepatic fat fraction categories ($\leq 10\%$, $>10\% - <21\%$, $\geq 21\% - <30\%$ and $\geq 30\%$), HbA1c group ($< 6\%$ and $\geq 6\%$), and ALT (greater or less than 1.5 x the upper normal limit) will be used to subgroup the analysis populations. Further, data from liver biopsies up to 6 months prior to screening will also be used to subgroup analysis populations based on fibrosis (0-1 vs. 2-3), NAS inflammation (0-1 vs. 2-3), and NAS ballooning (0-1 vs. 2). These will be used in addition to the main effects factors and the two-way interaction of those main effects.

In the primary analysis, any missing data will remain missing. Treatment effects between placebo and each of the active treatment groups within each of the hepatic fat and HbA1c categories will be generated and tested for significant differences between treatment and placebo using pre-specified contrasts.

To examine the effect of treatment within the various levels of these subgroup variables, a mixed models ANOVA will be employed if there are an appropriate number of observations in each cell (created by the crossing of study treatment and subgroup categories) and the data does not differ significantly from a normal distribution. In the event that this is not the case, the data will be ranked in an attempt to normalise it, and pairwise contrasts between treatment groups will be performed using Wilcoxon rank sum tests within each combination of visit and subgroup variable level will be performed. However, if the ranked data is also not normally distributed, a permutation test will be employed whereby the unranked data will be randomly sampled (Lehmann, 2006). No adjustment for multiple testing will be made. See Appendix 1 for more information on both the Wilcoxon rank-sum test and the permutation test.

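### If the rank or permutation fallback is used, Appendix 1 permutes within liver-fat category only and omits the diabetes/HbA1c randomisation factor; the test is then conservative to the extent that diabetes predicts the outcome

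*SAP*

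**What the plan says.** Protocol 8.1 allocates in permuted blocks and names two stratification factors. The first is diabetes: "Randomization will be proportional (1:1:1) and stratified by Baseline HBA1C", split at 6.0. The reason given is that "NASH without insulin resistance or diabetes may be clinically different to NASH with pre-diabetes or diabetes". The second is liver fat: "subjects will be stratified for baseline HFF according to the following groups", with cuts at 10%, 20% and 30%. The protocol synopsis lists the same two factors.

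SAP 7.2 analyses change in hepatic fat fraction by analysis of variance first. Ranks come in only when treatment-by-subgroup cells are too thin or the data are not normal: "In the event that this is not the case, the data will be ranked in an attempt to normalise it". If the ranks also fail the normality check, a permutation test follows. Appendix 1 gives the details of the rank and permutation procedure:

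- Step 1: "Each FF category at baseline will be defined as a separate cluster".
- Step 2 ranks within each such cluster. Steps 3 and 4 sum the active-arm ranks over clusters.
- The permutation is meant to "also protect the cluster design of the sample", and is carried out as follows: "Each permutation will be calculated by randomly sampling n_{i1} values within each cluster from the n_i values available".

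Diabetes/HbA1c does not appear in Appendix 1. In SAP 7.2 it appears only as one of several separate subgroup variables.

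**The concern.** A permutation test compares the observed statistic with its values under re-allocation. When allocation was stratified, the re-allocation should respect the same strata. Appendix 1 states that principle but applies it to one of the two factors. Within a fat category it exchanges labels freely between diabetic and non-diabetic patients, although the blocks had already roughly balanced the arms on diabetes. The reference distribution then includes between-stratum variation that the design largely removed from the real statistic. If diabetes status predicts the change in liver fat, that distribution is too wide, p-values are too large, and the benefit of having stratified on diabetes is lost. No pooled dose-placebo rank test elsewhere in the SAP conditions on both factors.

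**Working it through.** **The plan's own figure.** Protocol 12.1 assumes SD 6 at each time point and correlation 0.25. The SD of change is √(36 + 36 − 2 × 0.25 × 36) = 7.35, stated as 7.3. With 40 per arm, a difference of 5, SD 7.3 and two-sided 0.05, the noncentral t gives power 0.857, matching the stated 85% or so. The documents give no figure for the Appendix 1 test.

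**Mechanism.** For scores a in cluster i, the permutation variance is n_i0 n_i1 / [n_i (n_i − 1)] × Σ(a − ā)². If diabetes explains a share ρ of the within-category variance and allocation balances diabetes, the true null variance is about (1 − ρ) times this. Actual type I error is then about 2[1 − Φ(1.96/√(1 − ρ))] at nominal 5%. If a fraction π is diabetic and the strata differ by β points, ρ ≈ π(1 − π)β²/SD². With π = 0.5 and SD 7.3:

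- β = 2: ρ = 0.25 × 4/53.29 = 0.019, predicted level 0.048
- β = 3: ρ = 0.042, predicted 0.045
- β = 5: ρ = 0.117, predicted 0.037
- β = 7.3: ρ = 0.25, predicted 0.024

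**Simulation 1: total SD held at 7.3, nominal 5%, true effect -5.** There are 120 patients in three arms, with blocks of 6 within 4 fat categories × 2 diabetes strata. Assumptions not in the documents: half diabetic, fat mix 15/40/30/15%, block size. Each scenario used 6,000 to 30,000 runs. Here and below, 'cells' means the same fat-category ranks permuted within fat × diabetes cells.

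| β | Type I: Appendix 1 | Type I: cells | Power: Appendix 1 | Power: cells |
|---|---|---|---|---|
| 0 | 0.052 | 0.052 | 0.782 | 0.778 |
| 2 | 0.046 | 0.049 | 0.785 | 0.788 |
| 3 | 0.043 | 0.048 | 0.780 | 0.788 |
| 4 | 0.040 | 0.048 | 0.790 | 0.812 |
| 5 | 0.037 | 0.049 | 0.796 | 0.824 |
| 7.3 | 0.027 | 0.051 | 0.817 | 0.886 |

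The formula and the simulation agree closely. Ranking afresh in all eight cells gave power 0.761 at β = 0 and 0.769 at β = 2, which is 1 to 2 points below Appendix 1.

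**Simulation 2: residual SD held fixed, nominal 4.695% (the final level in SAP 9), true effect -4.** Change = −0.75 × (baseline − 20) + residual + β × diabetic + effect. The slope is 0.25 − 1 and the residual SD is 6√(1 − 0.25²) = 5.81. Assumptions: baseline mean 20, half diabetic, blocks of 6, normal residuals. Type I error is from two sets of runs (4,000 and 6,000); the power columns are from the set of 6,000.

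| β | Type I: Appendix 1 (two sets) | Power: Appendix 1 | Power: cells | Gain (second set in brackets) |
|---|---|---|---|---|
| 0 | 5.1%, 4.9% | 75.8% | 75.4% | −0.4 (−0.4) |
| 2 | 4.9%, 4.2% | 72.7% | 73.6% | +0.9 (+0.7) |
| 4 | 3.8%, 3.9% | 71.5% | 74.6% | +3.1 (+2.8) |
| 6 | 3.0%, 3.0% | 65.9% | 74.2% | +8.3 (+8.0) |

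Permuting within cells gave type I error of 4.4 to 4.9%. With 4,000 runs the simulation standard error near 5% is √(0.05 × 0.95/4000) = 0.34 points, so 5.1% against 4.7% is noise.

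**The case against.** **It is only a fallback.** This stands. The analysis of variance comes first, and a reader might infer that the primary analysis loses power whenever diabetes matters. SAP 7.2 does not support that. The fallback is not remote, however: 120 patients over 3 arms × 4 fat categories average 10 per cell, and the SAP defines neither an adequate cell size nor a normality test.

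**HbA1c is not ignored.** This also stands. SAP 7.2 plans contrasts within HbA1c categories and rank-sum tests within subgroup levels. What is missing is one pooled rank test that conditions on both factors.

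**The secondary endpoints.** SAP 7.3 runs them on the primary basis, so a reader might infer that HbA1c, glucose and HOMA-IR suffer most. The same section gives values measured at three or more time points a repeated-measures analysis with baseline as covariate, and these three qualify. At most the fallback could reach them, and the simulations do not cover them.

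**The diabetes effect is unknown.** Protocol 8.1 says only that the groups may differ. Differences of 4 to 6 points are about as large as the planned drug effect of 5. When diabetes explains less than about 4% of variance (a difference near 2.9 points), the loss is about 1 point or less. At the planned effect of -5 the loss can also be smaller: in one run of the second model with blocks of 3, power at β = 4 was 88.9% for Appendix 1 and 89.7% with eight plain rank cells. At β = 6 the figures were 86.6% and 90.4%.

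**Permuting within eight cells still ignores the blocks.** True, and the protocol gives no block size. The proposed cells match the stratification, not every detail of the allocation.

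**Conclusion.** The omission is real and its direction is clear. If the fallback is used, the Appendix 1 test stays within its nominal level apart from simulation error, and is conservative to the extent that diabetes predicts the outcome. The practical loss runs from nothing to about 1 power point for diabetes differences up to 2 points, to about 3 points at a difference of 4 and about 8 at a difference of 6, for a true effect of -4. These sizes rest on assumed diabetes effects, an even diabetes split, normal residuals and an assumed block size.

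A reader might take the mismatch to make the test invalid or its positive findings unreliable. The documents and the simulations do not support that, since no scenario showed inflated type I error beyond noise. Protocol 12 also describes the trial as exploratory, without multiplicity adjustment. This is a low-cost improvement to a conditional analysis.

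**What to change.** Leave step 2 of Appendix 1 (ranking within fat category) as it is. Change the permutation step so that arm labels are permuted only within the cells formed by baseline liver-fat category and diabetes stratum. A cell holding only one of the two arms compared contributes nothing. Re-ranking in all eight cells is not advised, because it costs 1 to 2 power points when diabetes is weakly related to the outcome.

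Define the strata as randomised. Protocol 8.1 cuts fat at 20% and HbA1c at ≤6.0 / >6.0, whereas SAP 7.2 cuts at 21% and <6 / ≥6. A patient at 20.5% fat or with HbA1c exactly 6.0 would change stratum. The protocol synopsis also places patients with a type II diabetes diagnosis in the diabetic stratum whatever their HbA1c, while Protocol 8.1 uses HbA1c alone. These definitions must be reconciled with what the randomisation system actually used.

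The cost is about 0.5 power points at most if diabetes is unrelated to the outcome, one revised step, a check of the stratum definitions and a few lines of code. Both factors are already recorded. The change should be made before any unblinding.

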#### Fat Liver Content Change from Baseline:

The current sample size of 40 subjects per group should yield approximately 85% power to detect a treatment effect of at least -5% with respect to the difference in the mean change from Baseline between one of the IMM-124E treatment groups and placebo assuming a standard deviation (SD) of 7.3% ( $\alpha=0.05$ ; two-tailed; unpaired t-test). The SD of 7.3% for the change from Baseline endpoint was derived assuming 1) SDs of 6% for each timepoint, 2) equal variances in each treatment group and 3) a low to moderate correlation of 0.25 between pre- and post-Baseline measurements.

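### SAP Appendix 1 adds unweighted rank sums over the liver-fat strata: a valid test, but less efficient for a common shift if the strata are unequal

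*SAP*

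**What the plan says.** SAP Appendix 1 compares each active arm with placebo in steps. Strata come first: "Each FF category at baseline will be defined as a separate cluster". Active and placebo values are ranked together within each stratum. The next step is "Calculate w_i which is the sum of ranks of the treatment group in each cluster separately". W is then the plain sum of the w_i over the M strata. W is tested by permuting within strata, with a normal approximation as the back-up. No reason is given for equal weights.

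SAP 7.2 turns to rank methods if cells are too sparse or the data are not normal. It describes Wilcoxon tests carried out separately at each visit and subgroup level. If the ranked data are also non-normal, it describes a permutation test on unranked values. It points to Appendix 1 for more on both.

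The fat categories differ between the documents. The protocol synopsis and section 8.1 cut at 10, 20 and 30%. SAP 7.2 uses 21% as the middle cut.

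The only power statement concerns a t-test (protocol 12.1): "The current sample size of 40 subjects per group should yield approximately 85% power". It is for a 5-point gap between one active arm and placebo, an SD of 7.3 and a two-sided 0.05 level. The synopsis adds that stratification was not allowed for.

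**The concern.** Ranks run from 1 to n_i within a stratum, so the scale of w_i grows with stratum size. In the plain sum, a stratum's treatment effect carries weight proportional to n_i0·n_i1. For a common shift the optimal weight is n_i0·n_i1/(n_i+1).

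Take two strata of 32 and 8 patients with balanced arms. The plain sum weights them 256 to 16, or 16:1, although one has only four times as many patients. The optimal weights are 256/33 = 7.76 to 16/9 = 1.78, or about 4.4:1. Patients in small strata contribute little.

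Each comparison has only about 80 patients. Four fat categories crossed with three arms make sparse cells likely, so SAP 7.2 may well reach its fallback methods. At stake is a few points of power on the primary endpoint.

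**Working it through.** **Planning figure.** With SD 6 at each time point and "a low to moderate correlation of 0.25 between pre- and post-Baseline measurements", the SD of change is √(2·36·0.75) = 7.35, which the protocol gives as 7.3. With 40 per arm, a difference of 5 and two-sided 0.05, power is 85.7% by the noncentral t (SD 7.3) and 85.2% with SD 7.35. The protocol's 85% reproduces. The SAP's final alpha is 0.04695; 0.05 is kept below to match the power statement.

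**Efficiency.** Arms are taken as equal within strata (protocol 8.1: "Equal numbers of patients in each treatment arm is targeted"), so a_i = n_i0·n_i1 = n_i²/4. Under a common shift, the efficiency of the plain sum relative to van Elteren is

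E = [(Σa_i)² / Σa_i(n_i+1)] ÷ Σ[a_i/(n_i+1)].

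Example with an assumed 10/40/40/10% split of 80 patients, so n_i = 8, 32, 32, 8 and a_i = 16, 256, 256, 16:
- Σa_i = 544
- Σa_i(n_i+1) = 144 + 8448 + 8448 + 144 = 17184
- Σa_i/(n_i+1) = 1.778 + 7.758 + 7.758 + 1.778 = 19.07
- E = (544²/17184)/19.07 = 17.22/19.07 = 0.90

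**Power, large-sample approximation.** z = k·√(12·S), with k = 5/(2·7.348·√π) = 0.192. S is 19.07 for van Elteren and E·19.07 for the plain sum; power is Φ(z − 1.96). For van Elteren, z = 0.192·√228.8 = 2.90, giving 83%.

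| Assumed split (%) | E | Plain sum | van Elteren |
|---|---|---|---|
| 5/45/45/5 | 0.94 | 80% | 83% |
| 10/40/40/10 | 0.90 | 79% | 83% |
| 10/45/35/10 | 0.89 | 78% | 83% |
| 15/50/25/10 | 0.84 | 76% | 83% |

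Simulating these splits gives values about one point lower: about 75 to 79% against about 82%.

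**Are unequal strata plausible?** Assume baseline fat is roughly normal with the protocol's SD of 6, and cut at 10, 20 and 30%.
- Mean 15: 20/60/20/1%, E = 0.84
- Mean 18: 9/54/35/2%, E = 0.90
- Mean 20: 5/45/45/5%, E = 0.94
- Mean 25: 1/20/60/20%, E = 0.84

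Four equal strata would need the quartiles at 10, 20 and 30, hence an SD near 10/0.674 = 14.8.

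**Non-constant effects.** Simulated power, plain sum / van Elteren, in percent: normal data, SD 7.3, 40,000 trials per scenario, permutation critical values. Effects run from the lowest to the highest fat stratum. Stratum sizes and effects are assumed.

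| Per-arm sizes | E | 5/5/5/5 | 0/6/6/0 | 1/4/6/8 | 8/4/4/8 |
|---|---|---|---|---|---|
| 10/10/10/10 | 1.00 | 81.7 / 82.3 | 36.7 / 37.6 | 75.4 / 76.4 | 92.3 / 92.7 |
| 6/14/12/8 | 0.94 | 79.5 / 82.8 | 72.2 / 60.9 | 78.0 / 81.0 | 76.3 / 86.5 |
| 4/16/14/6 | 0.90 | 78.0 / 82.9 | 83.2 / 73.9 | 76.3 / 81.8 | 66.1 / 80.7 |
| 3/20/12/5 | 0.86 | 76.3 / 82.2 | 85.7 / 79.6 | 69.1 / 79.9 | 62.1 / 77.7 |
| 2/18/18/2 | 0.94 | 79.9 / 82.9 | 91.3 / 88.9 | 79.6 / 81.9 | 62.2 / 71.1 |
| 28/4/4/4 | 0.80 | 73.7 / 82.8 | 5.0 / 8.9 | 9.8 / 25.9 | 98.2 / 98.6 |

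The small gaps in the first row come from the discreteness of the integer-valued plain sum. Rejection under no effect was 4.6 to 5.1% for both statistics.

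**The case against.** A reader might infer that van Elteren weights are better at no cost. The documents do not support this. The weights are optimal for a common shift, whereas SAP 2.2 expects response to differ between fat strata. If only the two middle strata respond and they are the large ones, the plain sum leads by 2.4 to 11.3 points in the table, and by up to about 13 in other simulated splits. This objection stands. However, SAP 2.2 gives no direction for the difference. Van Elteren leads when the effect rises with baseline fat, and leads by about 9 to 16 points in the same four splits when the effect is larger in the small outer strata.

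A reader might also infer that the primary p-value will come from this statistic. That is not settled. SAP 7.2 describes separate tests per subgroup level, which need no stratum weights, and then a permutation of unranked data. Appendix 1 describes one rank statistic pooled over strata and matches neither exactly.

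The fallback is meant partly for non-normal data, and there the cost is smaller. With heavy-tailed (t, 3 df) or exponential data of the same SD and a constant shift of 5, both statistics had 94 to 98% power in the unequal splits tabulated, and the gap was about 1 to 4 points.

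Finally, an unweighted sum is a legitimate stratified test, and the protocol calls the trial exploratory. Both points are correct and keep this a minor matter.

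**Conclusion.** The point holds as a minor matter of efficiency. Appendix 1 over-weights large fat strata relative to the optimum for a common shift and gives no reason for doing so. For plausible unequal strata the relative efficiency is about 0.84 to 0.94. With normal data and a 5-point shift this costs about 3 to 7 points of power (about 75 to 79% against about 82%). With equal strata the loss is nil.

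These figures rest on assumed stratum sizes, balanced arms within strata, no dropout and a constant effect. The protocol's SD of 6 with cuts at 10, 20 and 30% makes equal strata unlikely, but does not fix the sizes. The documents do not support reading this as an invalid test: both statistics hold their size. The gain from weighting depends on the effect pattern and can reverse.

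**What to change.** Before unblinding:

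1. Define step 4 of Appendix 1 as W = Σ w_i/(n_i+1), with the within-stratum permutation unchanged, and state the reason for the weights in one sentence. If the team expects the effect mainly in the largest strata, it should say so and justify the plain sum instead.
2. Take as clusters the fat categories used for randomisation, with the middle cut at 20% (protocol synopsis and 8.1) rather than 21% (SAP 7.2). Randomisation is also stratified by HbA1c. Crossing both factors would give up to eight clusters, on average 80/8 = 10 patients each per comparison; that scheme was not evaluated here.
3. Reconcile SAP 7.2 with Appendix 1: say whether the fallback is a set of tests per level, one pooled stratified rank test or a permutation of unranked values, and which gives the primary p-value.

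The cost is one formula and a few sentences, plus the possible power loss if the effect is confined to the largest strata.
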